5. STUDY POPULATION

The population that will be evaluated within the project is constitute by patients with diagnosed dementia with BPSD (diagnosis carried out using, according to Evidence Based Medicine, the neuropsychological tests below) and/or by patients who the diagnosis of dementia with BPSD will be performed at the Geriatric Competence Centre of the Clinica Luganese Moncucco.

The enrollment will be performed in May and June 2018.

All patients mentioned above, within 48 hours after the admission at the Geriatric Department or the manifestation of BPSD, will be assessed to neuropsychological and functional tests (CAM - Confusion Assessment Method -, CDR - Clinical Dementia Rating Score -, MMSE - Mini Mental State Examination -, FAB - Frontal Assessment Battery -, scala di Tinetti, BADL - Basic Activities of Daily Living -, IADL - Instrumental Activities of Daily Living -), as required by Good Clinical Practice[18]. Subsequently, patients who can be enrolled in the study will be randomized into two groups, described below.

Here is the study population on which we will focus:

GROUP A – **controls** -: will be enrolled 16 patients eligible for criteria of inclusion, treated with psychotropic drugs.

GROUP B – aromatherapy –: will be enrolled 16 patients eligible for criteria of inclusion, treated with psychotropic drugs and aromatherapy in air-diffusion.

Based on the randomization, patients will be divided into group A - controls - and group B - aromatherapy in air diffusion.

Neuropsychiatric Inventory (NPI) is a validated and useful tool for characterizing and assessing the BPSD frequency and seriousness.

A Resident Physician will perform the NPI in our study protocol.

The physician, by interview with patient's nurse, in absence of patient himself, will fill out the NPI-NH.

The above mentioned physician, formerly operating in the Geriatric Department – who knows the geriatric assessments - and currently active in the Rheumatology Department, will therefore respect the blind study procedure.

The geriatric nurse was chosen for the close relationship of care that is created with the patient; during the test, BPSD frequency and seriousness will be evaluated.

The psychological distress induced by BPSD patients, will be evaluated on the three figures who have in charge the patient, which are nurses, care assistants and the resident physicians.

The psychological distress assessment is part of the NPI-NH test with a scale of severity from 0 to 5.

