
Nurses will be undergo to NPI – NH test within 48 hours after patient admission or at first appearance of BPSD **(T1), T2 (T1-3 days)** 3 days after enrollment, at **T3 (T1-6 days)** 6 days after enrollment, at **T4 (T1-12 days)** at 14th day. According to the same timing, NPI-NH will also be performed to the resident physicians, the nurses and the care assistants to assess the psychological distress. The NPI-NH test will be performed following the Good Clinical Practice.

The tests results performed to the two groups of patients will be considered in order to assess a possible reduction in BPSD. As the project is a pilot study, a descriptive analysis will be performed.

Here the schemes defined for treatment with aromatherapy and psychotropic drugs, according to scientific publications in the first case and scientific publications and Evidence Based Medicine in the second:

Aromatherapy

Route of administration: air diffusion with ultrasonic diffuser in a single room and for about an hour.

Doses:

- Citrus sinensis: 6 drops at 8, 12 and 18 in nebulization

and

- Lavender angustifolia: 6 drops 8 p.m. in nebulization

PRN PSYCOPHARMACOTHERAPY

Drug:

- in case of psychomotor agitation:

Haloperidol 1 mg PO 10 times in 24 hours

1 mg SC/IM 5 times in 24 hours

Reperidone 0.5mg - 2mg PO in 24 hours *Olanzapine* 2.5 mg – 5 mg PO in 24 hours

Clozapine 6.25 mg – 25 mg PO in 24 hours

Quetiapine 12.5mg - 150mg PO in 24 hours

- in case of sleep disturbance:

Valerian 1 tb - 2 tbs PO in 24 hours Melatonin 1 tb - 2 tbs PO in 24 hours Lorazepam 0.5 mg - 3mg PO in 24 hours Oxazepam 7.5mg - 45mg PO in 24 hours Clomethiazole 1 tb -3 tbs PO in 24 hours - in case of anxiety/depression: Trazodone 25 mg – 150 mg PO in 24 hours Escitalopram 10 mg – 20 mg PO in 24 hours Mirtazapine 15 mg – 45 mg PO in 24 hours

Citalopram 10 mg - 20 mg PO in 24 hours

Paroxetine 20 mg – 50 mg PO in 24 hours

The control group is treated with psychopharmacological therapy, defined by the PI, according to the Evidence Based Medicine criteria.

Patient can withdraw the ICF at any time.

The investigators could decide to withdraw a patient for safety and health.

The withdrawn patients will not be evaluated unless they have been treated for 8 days, useful to evaluate the aromatherapy efficacy.

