8. PROJECT DESIGN

The project will be managed in the acute geriatric department of the Clinica Luganese Moncucco. Enrolment and treatment scheme is present in the flow chart (chapter 2).

After randomization patients will be enrolled in the two groups GROUP A, control group, and GROUP B, treatment group.

The enrollment will be performed in 2 months.

GROUP A: 16 patients, following the inclusion criteria, will be enroll and they will be treated with psychotropic drugs.

GROUP B: 16 patients, following the inclusion criteria, will be enroll and they will be treated with psychotropic drugs and, in a complementary way, with aromatherapy in environmental diffusion.

The project hypothesis will be validated using the following neuropsychological and functional tests:

- CAM (Confusion Assessment Method);
- CDR (Clinical Dementia Rating Score)
- MMSE (Mini Mental State Examination);
- FAB (Frontal Assessment Battery);

- Tinetti's scale;
- BADL (Basic Activities of Daily Living);
- IADL (Instrumental Activities of Daily Living);
- NPI-NH (Neuropsychiatric Inventory Nursing Home Version);

Neuropsychological tests are part of clinical practice [18].

Scientific reports show that essential oils in air diffusion are effective in 3 days. A final timepoints of 14 days represent the mean hospital stay:

2 days for the collection of behavioral data;

6 days to observe the possible effectiveness of aromatherapy in air diffusion;

6 days to adapt the therapy with oils and psychotropic drugs and stabilize patient's condition for a possible discharge.

Enrolled patients and nurses will be tested according to the following times:

8.1.1 Observation for 48 hours with data collection and execution of the NPI-NH (T1): in the 48 hours after patient admission at the Geriatric Department or at the diagnosis of dementia, the information collection will be performed: sensitive data (age, gender), dementia condition (CAM, CDR, MMSE, FAB), functional status (IADL, BADL, Tinetti scale) and the used number of psychotropic drugs. As a result of this evaluation, patient will be assessed for the presence of BPSD using the NPI-NH assessment scale, nurses will be undergo to NPI – NH test within 48 hours after patient admission. In case of a score greater than or equal to 1, patient will be followed within the study project, otherwise it will follow the standard process.

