8.1.2 Assessment of NPI-NH at T2 (T1-3 days): 3 days after enrollment, patient will be re-evaluated with NPI-NH to assess BPSD progress. In addition, the distress level of on the three health caregivers is also measured with the NPI-NH test.

8.1.3 Assessment of NPI-NH at T3, assessment of vital parameters and use of drug reserves (T1-6 days): 6 days after enrollment, NPI-NH will be re-executed, with associated assessment of patient's vital signs (PAS, PAM, FC) and the use of psychotropic drug reserves.

8.1.4 Final T4 assessment (T1-12 days): NPI-NH scale will be performed in association with vital signs.

The physician in charge of dispensing the NPI-NH questionnaires to nurses to collect BPSD patients status, will also submit the questionnaires to the referring physician, nurse and care assistants with the aim to assess the level of stress in the clinical staff (see "Distress" column in NPI-NH questionnaire in the appendix).

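### Vital signs are scheduled at T3 and T4 but not at T1, so the planned data allow no within-patient change, no imbalance check and no baseline adjustment

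*Protocol*

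**What the plan says.** Protocol section 8 itemises what is collected at each visit.

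- **T1 (8.1.1).** The list is "sensitive data (age, gender), dementia condition (CAM, CDR, MMSE, FAB), functional status (IADL, BADL, Tinetti scale) and the used number of psychotropic drugs", followed by the NPI-NH. Section 5 also describes this 48-hour assessment: patients "will be assessed to neuropsychological and functional tests", and the tests it names are cognitive and functional scales. Neither place mentions vital signs.
- **T2 (8.1.2).** "3 days after enrollment, patient will be re-evaluated with NPI-NH to assess BPSD progress"; staff distress is recorded as well. No vital signs.
- **T3 (8.1.3).** "NPI-NH will be re-executed, with associated assessment of patient's vital signs (PAS, PAM, FC) and the use of psychotropic drug reserves". This is the first mention of vital signs in the schedule.
- **T4 (8.1.4).** "NPI-NH scale will be performed in association with vital signs".

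The protocol does not expand PAS, PAM and FC; they are read here as blood pressure and heart rate. No ECG or laboratory test is scheduled in the available text. Section 8 refers to a flow chart in chapter 2 for the enrolment and treatment scheme, and that chart is not in the available text. Section 13 limits the statistics to description. The SAP analyses score changes from T1 to T3 and does not mention vital signs.

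**The concern.** A reading taken only at T3 and T4 has nothing before it to be compared with. A low pressure or fast pulse at T3 might be new, or might have been there when the patient entered the study. T4 minus T3 compares two values that both fall after enrolment.

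This matters more here for three reasons.

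- Fewer side effects of psychotropic drugs are part of the primary objective (section 6), and section 12 states that the oils carry no risk beyond hypersensitivity. Vital signs are the only scheduled physiological data that could bear on either statement.
- The SAP works with change from T1 to T3. Vital signs could not be summarised in that way.
- Imbalance at baseline did arise in this study. The SAP reports that the initial CIRS comorbidity index was slightly higher in the control group and adjusts for it. The scheduled data permit neither that check nor that adjustment for blood pressure or heart rate.

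**Working it through.** **1. Schedule, visit by visit**

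| Visit | Scheduled items (section 8.1) | Vital signs |
|---|---|---|
| T1 | Age, gender, CAM, CDR, MMSE, FAB, IADL, BADL, Tinetti, number of psychotropic drugs, NPI-NH | No |
| T2 | NPI-NH, staff distress | No |
| T3 | NPI-NH, vital signs, use of drug reserves | Yes |
| T4 | NPI-NH, vital signs | Yes |

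There are two scheduled vital-sign measurements per patient and no change scores from T1. Adding T1 gives three measurements and two change scores (T3 - T1 and T4 - T1).

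**2. The plan's own figure**

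Section 7 prints 8 blocks of 4, each with two A and two B: 8 × 4 = 32, with 16 per arm. This agrees with the stated sample size. No SD, correlation, alpha or power is given, so the rest is in SD units and the correlation is assumed.

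**3. What randomisation leaves to chance**

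Standard error of a difference between two means of 16 = sqrt(2/16) = 0.354 SD. Using the normal distribution, the probability that the arms differ at baseline by chance is:

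- more than 0.25 SD: 48.0%
- more than 0.50 SD: 15.7%
- more than 0.75 SD: 3.4%

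Without a T1 value, nobody can see which of these cases applies.

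**4. Precision of the arm difference at T3**

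Let r be the correlation between T1 and T3. The 95% half-width is 1.96 × standard error.

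- Level at T3 only: sqrt(2/16)
- Change score: sqrt(2/16) × sqrt(2 - 2r)
- Baseline-adjusted: sqrt(2/16) × sqrt(1 - r²), ignoring the small cost of estimating the slope

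| r (assumed) | Level only | Change score (ratio) | Adjusted (ratio) |
|---|---|---|---|
| 0.5 | 0.69 SD | 0.69 SD (1.00) | 0.60 SD (0.87) |
| 0.7 | 0.69 SD | 0.54 SD (0.77) | 0.49 SD (0.71) |

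At r = 0.5 a change score gains nothing between arms, while adjustment still does.

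**5. In clinical units (SDs assumed)**

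- Systolic pressure, SD 20 mmHg: 1.96 × 20 × 0.354 = ±13.9 mmHg unadjusted (10.4 to 17.3 for SD 15 to 25). Adjusted: 13.9 × 0.87 = ±12 and 13.9 × 0.71 = ±10 mmHg.
- Heart rate, SD 12/min: ±8.3/min unadjusted (6.9 to 10.4 for SD 10 to 15).

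**6. Timing of T3**

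The text places T3 "6 days after enrollment". Section 8 allows "6 days to observe the possible effectiveness of aromatherapy in air diffusion" after two days of data collection, so several days of exposure by T3 is a reasonable reading. The first diffusion is not dated relative to T1.

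**The case against.** The strongest case against is that this is a small gap in a measurement that no objective, statistical section or available SAP text uses, in a pilot meant to be descriptive. Several parts of that case stand.

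- **Flow chart.** Chapter 2 could show vital signs at T1. If it does, the defect becomes a mismatch with 8.1, which still needs correcting.
- **The T1 list may not be exhaustive.** The SAP uses an initial CIRS index that 8.1.1 does not list, so baseline items outside the list were obtained at least once. Ward charts may also hold admission readings. But nothing in the text says vital signs will be taken from them.
- **Control arm.** T1 records psychotropic drugs already in use, so a T1 reading is a study baseline and not a drug-free one.

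A reader might go further and infer any of the following; the documents do not support them.

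- *The trial's safety measure starts only after six days of treatment.* The protocol never calls vital signs a safety measure, and it dates T3 from enrolment.
- *The vital-sign data can say nothing about the oils.* Allocation is randomised, so arm differences at T3 and T4 are unbiased.
- *The span of about ±14 mmHg is the size of the defect.* It is ordinary sampling error with 16 per arm, and adjustment narrows it only to about ±10 to ±12.
- *Vital signs are also wrongly missing at T2.* The three-day figure in sections 5 and 8 concerns efficacy of the oils, so measuring at T2 is a matter of preference.

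What the objection does not remove is the loss of individual change. In a descriptive study of 32 patients, that is the most readable summary of such data.

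**Conclusion.** The point holds for the available text of section 8.1. Vital signs are scheduled at T3 and T4 and not at T1. The study-scheduled data therefore give no within-patient change from baseline in either arm, no view of baseline imbalance, and no baseline adjustment. The between-arm comparison of levels at T3 and T4 remains valid but is less precise: its standard error could have been 0.87 to 0.71 of its present size with adjustment. That range rests on an assumed correlation of 0.5 to 0.7, and the mmHg and per-minute figures rest on assumed SDs. The conclusion about the schedule needs neither assumption, but it is subject to what the chapter 2 flow chart shows. The gap is modest and cheap to close, and it does not affect the NPI-NH analysis.

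**What to change.** 1. Add PAS, PAM and FC to the T1 list in 8.1.1, taken before the first diffusion in Group B and at T1 in Group A.
2. Reconcile 8.1 with the chapter 2 flow chart.
3. Report individual change from T1 at T3 and at T4, by arm. Make any between-arm comparison baseline-adjusted, not a plain difference in change scores.
4. The SAP is written in the past tense, so patients have probably been enrolled already. For them, transcribe the last charted value before the first diffusion (Group B) or the value at T1 (Group A). Do not take the admission value automatically: section 9 allows enrolment when symptoms appear during the stay, and an admission reading may then predate T1.
5. If no such value can be recovered, state in the report that change from baseline in vital signs was not assessed.

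The cost is three extra fields on the T1 form. The values are assumed to be in routine ward charts, so no new procedure should be needed. The sample size does not change.

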9. ELEGIBILITY CRITERIA

Inclusion criteria:

- patients \geq 70 years;
- patients admitted to the Acute Geriatric Ward;

- patients with known diagnosis of dementia associated with BPSD or diagnosis performed during the hospitalization.

Exclusion criteria:

- patients with alcohol-based dementia;
- patients with Mild Cognitive Impairment (MCI) paragraph 4 -;
- patients with language barriers;
- patients already being treated with aromatherapy.

Patients admitted to the Geriatric Competence Centre of the Clinica Luganese Moncucco who do not respect inclusion criteria at the time of admission but develop them in the course of stay in the Clinic (for example: patient without psychological disorders and behavior at the entrance that manifest BPSD during hospitalization) could be enrolled.

10. CODIFY AND REGISTRATION PROCEDURES

A unique and increasing patient number (UPN) will be assigned to each patient. The clinical research unit of Clinica Luganese Moncucco will keep the dataset containing the correspondence between the UPN and the patient's personal and clinical data. All the analyzed data, available for scientific discussions or publishing, will be encoded.

11. PROJECT DURATION

Patients enrolment will be performed during May and June 2018.

12. RISKS AND BENEFITS

This project involves the use of essential oils, which are natural and with no collateral risks; the only risks the patient might present are hypersensitivity to essential oil [22].

If aromatherapy results efficacious in the management of BPSD, patients benefit would result in a reduction of the use of psychotropic therapy with a consecutive reduction in the side effects.

At the same time as the effectiveness of aromatherapy, possible benefits will also be available for caregivers (doctors, nurses, patient care assistant, family members).

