1. SYNOPSIS

The elderly patient demented in an acute geriatric department: pilot study, monocentric, randomized on the use of aromatherapy as a complementary treatment tool to psychopharmacology in psychological disorders and behavior (BPSD).

Rationale

Behavioral and psycological symptoms of dementia (BPSD) are a big issue for families, paramedics, physician and the patient itself (1,2,3,4).

In absence of universally recognized guidelines, the standard of treatment of these disorders involves the use of psychotropic drugs (typical/atypical neuroleptics, antidepressants, benzodiazepines) that are often found to have a reduce efficacy and induce a number of side effects such as sedation, impaired motor neurons slowdown, cardiac electrical alterations and extrapyramidal syndrome (5,6,7,8,9). In consideration of this, it is important to check for treating alternative ways, which can reduce psychological and behavioural disorders and at the same time can reduce the use of psychotropic drugs.

Concerning the aromatherapy [10], the therapeutic use of natural essential oils, there are decades of clinical experience, especially in France, accompanied by increasing scientific evidence with significant increase in publications regarding its use of psychological disorders and dementia-related behavior context (11,12,13,14).

Based on the available scientific publications, it has been therefore decided to use two essential oils (*Citrus sinensis, Lavandula angustifolia*) in environmental diffusion within the Geriatric Department of the Clinic Luganese Moncucco.

Objectives

Primary objectives: through the execution of the Neuropsychiatric Inventory – Nursing Home Version (NPI-NH), the neuropsychiatric and psychopathological symptoms of dementia patients will be evaluated in order to assess how the use of aromatherapy can improve the management of BPSD, reducing, where there is clinical indication, psychotropic therapy and secondary side effects. The score is considered positive if the presence of BPSD is greater than or equal to 1 (15, 16,17); the improvement of the score is represented from decrease of the NPI-NH respect to the initial assessment (19, 20).Performing neuropsychological tests is not an additional attention to enrolled patients, but it is part of clinical practice (18).

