4. PROTOCOL RATIONALE

Behavioral and psycological symptoms of dementia (BPSD) are a major problem for families, physicians and the patient itself [1,2,3,4].

Performing neuropsychological tests is not an additional source of distress for enlisted patients, but is part of clinical practice [18].

The standard treatment of these disorders involves the use of psychotropic drugs (typical/atypical neuroleptics, antidepressants, benzodiazepines) which are often ineffective and have a number of side effects such as sedation, reduction in cognitive performance, cardiac electrical alterations and extrapyramidal syndrome [5,6,7,8,9].

Within the scientific community, it is therefore mandatory to identify alternative ways of managing BPSDs, which can have a beneficial effect on patient life and, at the same time, a reduction in the used of psychotropic drugs.

The therapeutic use of natural essential oils has decades of clinical experience, especially in France, accompanied by an increase numbers of publications in their use in BPSD [11,12,13,14].

The knowledge of alternative treatments of BPSD (such as aromatherapy) are the basis of our study project, which involves the introduction of essential oils in the BPSD management, while maintaining conventional psychotropic therapy (typical/atypical neuroleptics, antidepressants, benzodiazepines) in a prefixed form of ProReNata (PRN) (paragraph 5).

The identified oils (*Citrus sinensis, Lavender angustifolia*) were selected on the degree of purity defined by the mass spectrophotometry available by the supplier.999

The choice of adjuvant therapy with essential oils could allow, in accordance with the 3rd principle of Medical Ethics to administer natural treatment to patients with distress with BPSD reducing, if possible, use of psychotropic drugs and their major side effects.

The use of essential oils in treatment of BPSD can also have a positive impact on patient economic management due to limited costs, allowing a distribution of treatments according to IV Principle of Ethics Medical: principle of justice.

Mild Cognitive Impairment (MCI) patients were excluded from the protocol as a form of predementia.[21].

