6. PROJECT OBJECTIVES

The goal of this project is to evaluate the effectiveness of aromatherapy in air diffusion in addition to psychotropic drugs in order to evaluate a possible reduction in BPSD.

The project's hypothesis is that GROUP B patients show an improvement in their BPSD. The performed neuropsychological tests will provide the answer to the project hypotesis.

Primary objectives: validate the hypothesis that the use of aromatherapy in air diffusion can improve the BPSD management, allowing a reduce in psychotropic therapy prescribed and its secondary side effects. The patient's nurses will be tested with NPI-NH, that will characterize

frequency and seriousness of BPSD [15,16, 17]. A score greater or equal to 1 is considered positive for presence of BPSD.

Secondary objectives: validate the hypothesis that the use of aromatherapy will improve the management of BPSD patients, with a simultaneously reduction of physicians, nurses and care assistants stress. The last aspect will be evaluated with a specific part of NPI-NH test. The decrease of the initial score represented an improvement [19.20]. The NPI-NH test will be performed according to the time points defined in paragraph 7.1.1

The obtained results could be interesting to the future implementation of the use of essential oils in air diffusion in acute geriatric departments and in all facilities with BPSD patients.

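### The side-effect clause of the primary objective and the one named risk of the oils have no listed data collection, so neither can be reported by arm

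*Protocol*

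**What the plan says.** Both statements of the primary objective go beyond BPSD. The synopsis speaks of "reducing, where there is clinical indication, psychotropic therapy and secondary side effects", and section 6 of "allowing a reduce in psychotropic therapy prescribed and its secondary side effects". Section 4 says which effects are meant: "side effects such as sedation, reduction in cognitive performance, cardiac electrical alterations and extrapyramidal syndrome". The measure attached to the objective is the NPI-NH. Section 6 puts it this way: "The patient's nurses will be tested with NPI-NH, that will characterize" how often BPSD occur and how serious they are.

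Section 12 names a single risk of the intervention: "the only risks the patient might present are hypersensitivity to essential oil". Section 9 lists four exclusions: alcohol-related dementia, MCI, language barriers, and "patients already being treated with aromatherapy". None concerns allergy or hypersensitivity.

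Section 8.1.1 lists the T1 data: age, gender, cognitive tests, "functional status (IADL, BADL, Tinetti scale) and the used number of psychotropic drugs", then the NPI-NH. For T3, section 8.1.3 says that "NPI-NH will be re-executed, with associated assessment of patient's vital signs (PAS, PAM, FC) and the use of psychotropic drug reserves". Section 5 lets the investigators withdraw a patient for safety, and leaves withdrawn patients out of the evaluation unless they have had 8 days of treatment.

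**The concern.** A stated part of the primary objective needs a measurement, and the schedule does not appear to contain one. The same holds for the one harm that the protocol expects the oils might cause.

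Two conclusions are at stake. If drug use falls in the aromatherapy group, the report may be tempted to claim fewer side effects as well, with nothing observed to support it. And if no reactions are reported, that silence may be read as safety when it reflects only that nobody was asked to write them down. Patients with dementia may not report a reaction themselves. Section 6 looks ahead to use in other facilities, and section 15 commits to publication, so the statement on harm will be read beyond this ward.

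**Working it through.** The plan gives no figure for harm or side effects, so there is none to reproduce. The check is a reading of each visit, followed by a short calculation of what 16 treated patients could show.

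**1. Visit by visit (section 8, with the staff-distress timing from section 5)**

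| Visit | Listed data | Section 4 side effects | Reactions to oils |
|---|---|---|---|
| T1 | Age, gender; CAM, CDR, MMSE, FAB; IADL, BADL, Tinetti; number of psychotropic drugs; NPI-NH; staff distress | Not listed | Not listed |
| T2 | NPI-NH; staff distress | Not listed | Not listed |
| T3 | NPI-NH; staff distress; vital signs; reserve drug use | Not listed | Not listed |
| T4 | NPI-NH; staff distress; vital signs | Not listed | Not listed |

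**2. Could a listed item stand in for side effects?**

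- CAM, MMSE, FAB and Tinetti could reflect sedation, cognitive or motor effects. They are scheduled only at T1, so no change can be calculated.
- Vital signs are listed at T3 and T4 without a T1 value. They do not measure sedation, cognition, cardiac electrical changes or extrapyramidal signs.
- The NPI-NH sleep domain includes excessive daytime sleep, but scores it as a symptom. Drug sedation and BPSD cannot be separated.
- The number of drugs (T1) and reserve use (T3) bear on drug exposure, not on its effects.

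**3. Withdrawals.** Safety withdrawal is at the investigators' discretion, and no reason has to be recorded. A patient who reacted early and was withdrawn before 8 days would leave the evaluation.

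**4. Analysis.** Protocol section 13 promises description only. The SAP text analyses changes in scores from T1 to T3 and contains no side-effect or harm analysis.

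**5. What recording could show.** Section 7 gives 8 blocks of 4, so 32 patients, 16 per group. If reactions were recorded and none occurred in the 16 treated patients, the exact upper bound solves (1 − p)^16 = α:

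- one-sided 95%: 1 − 0.05^(1/16) = 1 − 0.829 = 17.1%
- two-sided 95%: 1 − 0.025^(1/16) = 1 − 0.794 = 20.6%

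The chance of seeing at least one reaction is 1 − (1 − p)^16. The documents give no reaction rate, so the rates here are assumptions:

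| Assumed true rate | Chance of at least one reaction in 16 |
|---|---|
| 1% | 15% |
| 2% | 28% |
| 5% | 56% |
| 10% | 81% |

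These figures describe the trial after the fix. Without recording, not even this coarse bound is available.

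**The case against.** The strongest reply is that side-effect reduction is not a free-standing objective. Both statements tie it to reduced psychotropic therapy, and section 12 presents it as following from lower drug use. The named measure, the NPI-NH, is collected at all four visits. This stands as a limit on scope. A reader might infer that the whole primary objective cannot be answered, and the documents do not support that: the gap concerns one derived clause. But lower drug use does not by itself show fewer side effects, and the clause appears in both statements.

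A second reply is that safety observation exists: vital signs at T3 and T4, safety withdrawal, and a declared adherence to GCP in section 14. That is correct, so it would be wrong to say that safety is not observed at all. None of these, however, specifies what is recorded, when, or how it is reported by arm.

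A reader might also take section 12 as contradicting itself, since it denies collateral risks and then names one. Its natural reading is that there are no risks except hypersensitivity. Likewise, the missing criterion in section 9 is an omission from the listed criteria. It does not prove that the risk is ignored, because it may be handled at consent or by clinical judgement. The consent pages and the chapter 2 flow chart were not available for this check; section 8 describes the chart as an enrolment and treatment scheme.

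Finally, collecting side effects has limits. Cardiac electrical changes cannot be excluded without a test that is not scheduled, and sections 1 and 3 promise no additional tests. An item on reactions to diffusion could also reveal allocation to the physician who conducts the NPI-NH interview. Both points stand and shape the fix.

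**Conclusion.** The point holds for the side-effect clause and for reactions to the oils. Following the plan exactly yields no listed data on either, and an early reaction leading to withdrawal would be lost from the evaluation. The trial could therefore neither support a statement about fewer side effects nor report harm by arm. The NPI-NH part of the objective is untouched.

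The gain from correcting this is real but modest: with complete recording, zero reactions in 16 patients would still be compatible with a rate of up to 17.1% (one-sided) or 20.6% (two-sided). Those bounds assume that all 16 treated patients are observed and counted. The conclusion also assumes that the flow chart adds no data collection beyond section 8. For a small descriptive pilot this should be fixed, but it does not invalidate the trial.

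**What to change.** 1. At T1 to T4, in both groups, have ward staff record from existing ward notes any suspected reaction, any noted psychotropic side effect of the kinds listed in section 4, and the reason for any withdrawal. Keep this record separate from the NPI-NH interview, so that the blinded physician neither completes nor sees it.
2. Report counts by arm with exact 95% confidence intervals for all randomised patients, including those withdrawn before day 8.
3. State that effects needing an unscheduled test, such as cardiac electrical alterations, are captured only if clinically noted, and that absence from the notes does not show absence of the effect.
4. If this is not done, remove the side-effect clause from the primary objective and say in the report that harms were not assessed. The SAP is written in the past tense, so if the visits are already complete, the equivalent is extraction from the charts by arm, or that same statement.
5. Ask the investigators to reconcile the eligibility list in section 9 with the risk named in section 12. How to do so is theirs to decide.

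The cost is a small amount of chart recording per visit and some wording, with no extra test. The downside is incomplete capture, which item 3 discloses.
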